#### 9.1.3.3 Days 7 ( $\pm 2$ days), 14 ( $\pm 2$ days), and 30 ( $\pm 3$ days)

Subjects will return for follow up visits on **Days 7, 14, and 30** after treatment, with repeat examinations, blood and urine work as outlined below.

The following assessments will occur at this visit:

- Medical history
- Concomitant Medications
- Adverse Events
- Physical Exam
- Vital Signs (heart rate, respiratory rate, temperature, weight, height (see Section 10.5 for more details), and blood pressure)

The following blood lab work will occur at this visit:

- Complete blood cell count (CBC) and differential, platelets
- Aspartate aminotransferase (AST)/alanine transaminase (ALT)
- Gamma-glutamyl transpeptidase (GGT)\*
- A Comprehensive Metabolic Panel (CMP) that includes:
  - o Albumin/Serum total protein
  - o Serum total bilirubin
  - Electrolytes
  - o Calcium
  - o Creatinine/Blood Urea Nitrogen (BUN)
  - o Serum glucose
  - Alkaline phosphatase
- Prothrombin time (PT)/activated partial thromboplastin time (PTT)/INR
- Amylase
- Creatine kinase (CK)
- Total IgG (Day 30 only)
- Direct Bilirubin
- ELISpots for T-cell responses to AAV9 and Dystrophin
- Blood for vector shedding studies (see Section 10.4 for details)

The following urine lab work will occur at this visit:

Urinalysis

\* For subjects taking drugs that potentially induce GGT synthesis through the cytochrome P450 system, the clinically significant range will be estimated starting at two times the levels obtained from the baseline screening test and up.

- Urine for biobanking
- Urine for vector shedding studies (see Section 10.4 for details)

The following additional samples will be collected for vector shedding studies (see Section 10.4 for details):

- Saliva
- Feces

On **Day 7**, additional tests will include complement studies, consisting of Sc5b-9, C3, C4, and CH50.

On **Day 30**, additional tests will include an ELISA for detection of total antibodies to AAV9, Cystatin C, and whole blood banking.

## 9.1.3.4 Days 45, 75, 120, 150, and 2 weeks after return of prednisone dose to baseline ( $\pm 3$ days)

For convenience, for subjects outside of the Columbus area, these may be locally drawn and shipped to the NCH clinical laboratory.

*The following blood lab work will occur at this visit:* 

- Aspartate aminotransferase (AST)/alanine transaminase (ALT)
- Gamma-glutamyl transpeptidase (GGT)\*
- A Comprehensive Metabolic Panel (CMP) that includes:
  - o Albumin/Serum total protein
  - o Serum total bilirubin
  - Electrolytes
  - o Calcium
  - o Creatinine/Blood Urea Nitrogen (BUN)
  - Serum glucose
  - Alkaline phosphatase
- Prothrombin time (PT)/activated partial thromboplastin time (PTT)/INR
- Total IgG (Day 120, 150)
- Direct Bilirubin

## 9.1.3.5 Day $60 (\pm 7 days)$

The following assessments will occur at this visit:

- Medical history
- Concomitant Medications
- Adverse Events
- Physical Exam
- Vital Signs (heart rate, respiratory rate, temperature, weight, height (see Section 10.5 for

\* For subjects taking drugs that potentially induce GGT synthesis through the cytochrome P450 system, the clinically significant range will be estimated starting at two times the levels obtained from the baseline screening test and up.

#### more details) and blood pressure)

The following blood lab work will occur at this visit:

- Complete blood cell count (CBC) and differential, platelets
- Aspartate aminotransferase (AST)/alanine transaminase (ALT)
- Gamma-glutamyl transpeptidase (GGT)\*
- A Comprehensive Metabolic Panel (CMP) that includes:
  - Albumin/Serum total protein
  - Serum total bilirubin
  - Electrolytes
  - o Calcium
  - o Creatinine/Blood Urea Nitrogen (BUN)
  - Serum glucose
  - Alkaline phosphatase
- Prothrombin time (PT)/activated partial thromboplastin time (PTT)/INR
- Creatine kinase (CK)
- Total IgG
- Direct Bilirubin
- ELISA for detection of total antibodies to AAV9
- ELISpots for T-cell responses to AAV9 and Dystrophin
- Whole blood for biobanking
- Blood for vector shedding studies (see Section 10.4 for details)

The following urine lab work will occur at this visit:

- Urinalysis
- Urine for biobanking
- Urine for vector shedding studies (see Section 10.4 for details)

The following additional samples will be collected for vector shedding studies (see Section 10.4 for details):

- Saliva
- Feces

# 9.1.3.6 Day 90 ( $\pm$ 7 days) and 180 ( $\pm$ 14 days), and Months 12 ( $\pm$ 14 days), 18 ( $\pm$ 14 days), and 24 ( $\pm$ 14 days) visits

The following assessments will occur at these visits:

- Medical history
- Concomitant Medications

\* For subjects taking drugs that potentially induce GGT synthesis through the cytochrome P450 system, the clinically significant range will be estimated starting at two times the levels obtained from the baseline screening test and up.

- Adverse Events
- Physical Exam
- Vital Signs (heart rate, respiratory rate, temperature, weight, and blood pressure, height (see Section 10.5 for more details))
- ECHO
- ECG
- Functional tests (variable depending on age of enrollment)
  - Enrollment age:  $\leq$  36 months
    - Bayley-IV scores (Bayley Scales of Infant and Toddler Development)
  - o Enrollment age: > 36 months and < 5 years of age
    - North Star Ambulatory Assessment (NSAA)
    - Time to climb 4 stairs
    - Amount of time required to walk 100 meters (100MWT)
    - -
  - Enrollment age:  $\geq$  5 years old until Non-Ambulant
    - North Star Ambulatory Assessment (NSAA) score
    - Time to climb 4 stairs
    - Amount of time required to walk 100 meters (100MWT)
    - Force generated in knee flexion and extension in maximum voluntary isometric contraction (MVICT).
- Pulmonary functional test (PFT) (see Section 10.3 for more details)

The following blood lab work will occur at this visit:

- Complete blood cell count (CBC) and differential, platelets
- Aspartate aminotransferase (AST)/alanine transaminase (ALT)
- Gamma-glutamyl transpeptidase (GGT)\*
- A Comprehensive Metabolic Panel (CMP) that includes:
  - o Albumin/Serum total protein
  - o Serum total bilirubin
  - Electrolytes
  - o Calcium
  - Creatinine/Blood Urea Nitrogen (BUN)
  - Serum glucose
  - Alkaline phosphatase
- Prothrombin time (PT)/activated partial thromboplastin time (PTT)/INR
- Creatine kinase (CK)
- Cystatin C
- Total IgG
- Direct Bilirubin
- ELISA for detection of total antibodies to AAV9
- ELISpots for T-cell responses to AAV9 and Dystrophin
- Blood for vector shedding studies (see Section 10.4 for details)
- \* For subjects taking drugs that potentially induce GGT synthesis through the cytochrome P450 system, the clinically significant range will be estimated starting at two times the levels obtained from the baseline screening test and up.

The following urine lab work will occur at this visit:

- Urinalysis
- Urine for biobanking
- Urine for vector shedding studies (see Section 10.4 for details)

The following additional samples will be collected for vector shedding studies (see Section 10.4 for details):

- Saliva
- Feces

At the Day 90 and 180 and the Month 12, either an open or needle muscle biopsy will occur (see Section 10.1 for more details). Additionally, at the Day 180, and Months 12, 18 and 24 month visits, MRI imaging will also be performed (*see Section 10.2 for more details*)

# 9.2 Schedule of Events

**Table 8: Schedule of Events** 

U7.ACCA STUDY TIMELINE																			
Study Interval	Screening 	Pre Infusion Visit	Hospital Admission Vector Injection	Inpa	tient	Follow-Up (Outpatient)													
Visit#	Visit 1  & 2		Visit 3 			Visit 4	Visit 5	Visit 6	Labs 	Visit 7	Labs 	Visit 8 	Labs 	Labs 	Labs 	Visit 9 	Visit 10 	Visit 11 	Visit 12 
Study Procedures	Days -45 to -1	Day -1	Day 0	Day 1	Day 2	Day 7	Day 14	Day 30	Day 45	Day 60	Day 75	Day 90	Day 120	2 wks post steroid return	Day 150	Day 180	Month 12	Month 18	Month 24
Informed consent 	X																		
Informed assent 	X																		
Medical History	X	X	X	X	X	X	X	X		Х		X				X	X	X	X
Concomitant medications	X	X	X	Х	Х	X	X	Х		Х		X				X	X	X	X
Adverse events		X	X	X	X	X	X	Х		Х		X				X	X	X	X
Physical exam	X	X	X 	X	X	X	X	Х		X		X				X	X	X	X
Vital signs	X	X	X 	X	X	X	X	X		X		X				X	X	X	X
Height	X	X				X	X	X		X		X				X	X	X	X
Weight	X	X				X	X	X		X		X				X	X	X	X
MRI 	X															X	X	X	X
ECHO	X											X				X	X	X	X
EKG	X											X				X	X	X	X
Bayley-IV 	X											X				X	X	X	X
NSAA/NSAA-Revised 	X											х				Х	Х	Х	x
Time to climb 4 stairs 	X											х				Х	Х	X	x
100 m walk/run 	X											х				Х	Х	X	x
MVICT 	x											X				Х	X	X	х
PFTs/Spirometry 	x											X				X	X	X	х
Muscle Biopsy 	X											X				X	X		
Anaesthesia 	X		x									X				X	X		
CBC/Diff	X	X	^	X		x	x	x		х		X				X	X	X	х
AST/ALT	X	X		X		X	X	X	х	X	X	X	X	X	x	X	X	X	X
Serum GGT	x	x		X		X	X	X	X	X	X	X	X	X	X	X	X	X	X
CMP	x	X		X		X	X	X	X	X	X	X	X	X	X	X	X	X	X
PT/PTT/INR	x	X		X		X	X	X	X	X	X	X	X	X	X	X	X	X	X
Amylase	X					X	X	Х											
CK	X	X		Х		X	X	Х		Х		х				X	X	X	х
Cystatin C	X							Х				X				X	Х	X	x
Total IgG	x							Х		Х		х	X		Х	X	Х	X	х
D-Dimer	X																		
Direct Bilirubin	X	X		х		х	х	Х	х	х	х	х	х	Х	Х	Х	Х	Х	x
SC5b-9, C3, C4, CH50	Х					X													
Antibody testing Hep. B, C and	X																		
ELISA	X							X		Х		X				X	X	X	Х
ELISpot	X	X				X	Х	Х		Х		Х				Х	Х	X	Х
Whole Blood Banking		X						Х		Х									
Vector Shedding Studies 	х		X 	X	X	X	X	Х		Х		X				Х	Х	X	Х
Urinalysis	х			х		X	X	х		Х		X				Х	Х	X	Х
Urine Banking	х			X	X	X	X	Х		Х		X				Х	Х	X	Х
Steroid Administration 		х	X	х	Х	X	X	Х	Х	Х	Х	X	X						
Admit to Hospital			X																
Study agent administration			X																

#### **TABLE 8 FOOTNOTES**

- 1. If there are changes to the study, parents or subjects will be re-consented or re-assented at their next visit.
- 2. Visit will occur over multiple days.
- 3. Muscle strength testing at baseline (days -45 to -1) and visits 8-10 will be performed at least 1 day preceding the biopsy.
- 4. An open muscle biopsy will be peformed on one leg at the baseline, and on the other leg at 3 months post gene transfer. Needle muscle biopsy will be performed in either leg at 6 months and the contralateral at 12 months. Biopsies must be performed after the strength evaluation and lab tests. See section 12.1 for more details.
- 5. Prophylactic prednisolone/prednisone as well as Proton Pump Inhibitor (PPI) begins on Day -1 and is tapered according to AST, ALT, and ELISpot results starting at Day 30. Anticipate that most subjects will be on prednisolone for up to 120 days.
- 6. Day 0 physical exam will consist of the anesthesia evaluation prior to sedation or by study team if sedation is not required.
- 7. Day 0 Vital Signs (Heart rate, respiratory rate, pulse oximetry (only if sedated), temperature, and blood pressure) will be measured as per Section 9.1.2.2.
- 8. Samples scheduled in between f/u visits will be collected locally and shipped to us.
- 9. Depending on the age of subject, there may be sedation required for gene therapy and needle biopsies. This determination will be at the discretion of the Pl.
- 10. The functional testing administered will be determind by the age of the subject.
- 11. In order to avoid the risk of sedation for an exploratory efficacy measure, muscle MRI will not be performed in any subjects who are unable to remain still for a MRI without sedation. To evaluate if a subject will be able to remain still for a MRI, a mock MRI will be given at the screening visit.
- 12. Vector shedding analysis post dosing will be performed on DNA isolated from different biological fluids (plasma, urine, saliva and feces) until three consecutive samples are negative for the presence of viral DNA for each specimen type.
- 13. Vector Shedding on day 0 will be collected at 4 and 8 hours post gene transfer.
- 14. If the subject is too young to reliably rest these values, it will not be performed and will not be recorded as a protocol deviation.
- 15. For children under 10 kg in weight, the blood draw schedule will be reviewed to limit blood draw volumes to ≤ 3% of total body weight over a 24 hour period and ≤ 10% of total body weight over a 30 day period.

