**Table 2: Revision Record** 

Protocol Version	Description of Changes
V1.0 25Oct2019	Removed control group and dose escalation from trial.
	
 
Added RT-PCR measurement of exon 2 exclusion from dystrophin mRNA transcript to secondary outcomes.
 

	
 
Moved RNASeq analysis of exon 2 exclusion from dystrophin mRNA transcript to exploratory outcomes.
 

	• Changed inclusion criteria to greater than 6 months and less than 14 years.
	
 
Removed Western Blot analysis at days 90 and 180 as well as 12 months for dystrophin associated protein complex.
 

	
 
Removed Leukocyte marker analysis at days 90, 180, and 12 months.
 

	• Added language to indicate report of non-life threatening SAEs and DLTs to the IRB within 15 calendar days.
	
 
Added possibility of moving blood tests to other days of the visit if the child is under 10kg and may have too much blood drawn.
 

	
 
Added language to clarify the expected elevations in AST/ALT levels for the DMD population.
 
Clarified that Dose-Limiting Toxicity events must be unexpected to be considered as such.
 
Added Hepatology to the fields of expertise of the DSMB members.
 
Added language to allow for weekly blood tests past 30 days post-infusion if the subject's AST/ALT levels have not returned to baseline and the prednisone/prednisolone dose is maintained rather than decreased back to the standard clinical dose.
 
Removed specification of the antibody used for
 

	
 
immunofluorescence staining and western blot.
 
Updated CTCAE referenced to v5.0.
 

	
 
Changed [name] from Principal Investigator to Sponsor Investigator.
 

	• Changed the N from N=3 to N=1-3.
V1.0 13Dec2019  V2.0 20Jan2020	
 
Added labs for Total IgG, D-Dimer, Direct Bilirubin, SC5b-9, C3, and C4 at screening
 
Added Total IgG at Day 30, 60, 90, 120, 150, 180, Month 12, Month 18, Month 24
 
Added Direct Bilirubin to Day -1, 1, 7, 14, 30, 45, 60, 75, 90, 2 weeks post steroid, 120, 150, 180, Month 12, Month 18, Month 24
 
Removed redundancies in the Safety Reporting section.
 
Added [name], [name], [name], and [name] as Co-Investigators.
 

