## 6.3 Number of Subjects

Up to 3 DMD subjects matching the inclusion/exclusion criteria will be enrolled. Enrollment will be proceed as outlined in Section 6.4.

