#### Exclusion Criteria

- 1. Active viral infection based on clinical observations.
- 2. Symptoms or signs of cardiomyopathy, including:
  - a. Dyspnea on exertion, pedal edema, shortness of breath upon lying flat, or rales at the base of the lungs
  - b. Echocardiogram with ejection fraction below 40%
- 3. Serological evidence of HIV infection, or Hepatitis B or C infection
- 4. Diagnosis of (or ongoing treatment for) an autoimmune disease
- 5. Persistent leukopenia or leukocytosis (WBC  $\leq$  3.5 K/ $\mu$ L or  $\geq$  20.0 K/ $\mu$ L) or an absolute neutrophil count < 1.5K/ $\mu$ L
- 6. Concomitant illness or requirement for chronic drug treatment that in the opinion of the SI creates unnecessary risks for gene transfer
- 7. AAV9 binding antibody titers  $\geq 1:400$  as determined by ELISA immunoassay
- 8. Abnormal laboratory values in the clinically significant range in Table 7, based upon normal values in the Nationwide Children's Hospital Laboratory

Table 7: Normal and abnormal laboratory values at Nationwide Children's Hospital Laboratory

System	Assay	Normal Range	Abnormal (Clinically Significant)
Liver Function	GGT	8-80 U/L	>80 U/L
	Total Bilirubin	0.1-1 mg/dL	≥3 mg/dL
	Direct Bilirubin	<0.6 mg/dL	>2 mg/dL
Renal Function	Cystatin C	0.3-1.3 mg/dL	>1.8 mg/dL
Hematologic Hemoglobin		(g/dL) 2 – 6 yrs: 11.5-13.5 6 – 12 yrs: 11.5-15.5	For all ages: $\leq 8 \text{ or } \geq 18 \text{ g/dL}$
		13-18 years: 13-15	-

Hematologic	White Blood Cells	4 – 6 yrs: 5.5-15.5 6 – 10 yrs: 5-14.5 10 – 21 yrs: 4.5-13.5	For all ages: White blood cell count $\leq 3.5 \text{ or } \geq 20 \text{ x } 10^3$ cells/mL OR Absolute neutrophil count of $\leq 1.5 \text{ x } 10^3 \text{ cells/mL}$
-------------	----------------------	--	--

\* For Hemoglobin, subjects will be excluded if they have a value less than the lower limit of normal for age at screening regardless of age. Abnormal but not clinically significant hemoglobin levels may be repeated during the screening period, and the subject accepted for enrollment if the results are not less than the lower limit of normal.

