## 9.1 Study Visits

### 9.1.1 Screening (day -45 to day -1)

Informed consent will be obtained prior to the collection of any data and any study related procedures. Baseline measures from subjects will be obtained prior to gene transfer and will occur over two visits (up to 3 weeks apart). Because a pre-existing antibody response would be exclusionary, ELISA and ELISpot testing will be performed at the first visit, allowing the results to be reviewed prior to the open muscle biopsy and its subsequent risks (including sedation). The weight obtained at screening will be used to calculate the viral vector dose.

The following assessments will occur at these visits:

- Informed Consent
- Assent, if applicable
- Medical history
- Concomitant Medications
- Physical Exam
- Vital Signs (temperature, respiratory rate, heart rate, blood pressure, height (see Section 10.5 for more details), and weight)
- MRI of the lower legs (see Section 10.2 for more details)
- ECHO
- ECG
- Functional tests (variable depending on age of enrollment)
  - Enrollment age:  $\leq$  36 months
    - Bayley-IV scores (Bayley Scales of Infant and Toddler Development)
  - o Enrollment age: > 36 months and < 5 years of age
    - North Star Ambulatory Assessment (NSAA)

- Time to climb four stairs
- Amount of time required to walk 100 meters (100MWT)
- Enrollment age:  $\geq$  5 years old until Non-Ambulant
  - North Star Ambulatory Assessment (NSAA) score
  - Time to climb four stairs
  - Amount of time required to walk 100 meters (100MWT)
  - Force generated in knee flexion and extension in maximum voluntary isometric contraction (MVICT).
- Pulmonary functional tests (PFTs), including forced vital capacity. (See Section 10.3 for more details.)
- Open Muscle Biopsy (For details, see Section 10.2)

The following blood lab work will occur at this visit. (Lab work may be drawn over several days during visit if deemed necessary by study team except as noted above for ELISA and ELISpot.)

- Complete blood cell count (CBC) and differential, platelets
- Aspartate aminotransferase (AST)/alanine transaminase (ALT)
- Gamma-glutamyl transpeptidase (GGT)\*
- A Comprehensive Metabolic Panel (CMP) that includes:
  - Albumin/Serum total protein
  - Serum total bilirubin
  - Electrolytes
  - o Calcium
  - o Creatinine/Blood Urea Nitrogen (BUN)
  - Serum glucose
  - Alkaline phosphatase
- Prothrombin time (PT)/activated partial thromboplastin time (PTT)/INR
- Amylase
- Creatine kinase (CK)
- Cystatin C

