- Total IgG
- D-Dimer\*\*
- Direct Bilirubin
- SC5b-9\*\*
- C3, C4\*\*
- CH50\*\*
- Antibody testing for Hepatitis B, C and HIV
- ELISA for detection of total antibodies to AAV9
- ELISpots for T-cell responses to AAV9 and Dystrophin
- Blood for vector shedding studies

\* For subjects taking drugs that potentially induce GGT synthesis through the cytochrome P450 system, the clinically significant range will be estimated starting at two times the levels obtained from the baseline screening test and up.

\*\* These laboratory tests have been recommended by the DSMB to be obtained at screening. These will not necessarily be exclusionary but having a baseline value will be helpful for comparison if a subject were to have any platelet or renal abnormalities that may be immune mediated after gene transfer.

The following urine lab work will occur at this visit:

- Urinalysis
- Urine for biobanking
- Urine for vector shedding studies

The following additional samples will be collected for vector shedding studies:

- Saliva
- Feces

For children under 10 kg in weight, the blood draw schedule will be reviewed to limit blood draw volumes to  $\leq 3\%$  of total body volume over a 24 hour period and  $\leq 10\%$  of total body volume over a 30 day period. The study team may deem it necessary to move or remove non-safety-related blood draws to other days if the volume drawn in one 24-hour period will be too near to 3% of total body volume.

Repeat testing of laboratory abnormalities within the screening period: Given the biologic variability inherent in some laboratory testing results, we will retest subjects with minimal and not clinically significant abnormalities resulting in values outside the NCH lab's normal range as defined by Table 7, such as minimal abnormalities of hemoglobin or CBC values. Similarly, subjects with anti-AAV9 endpoint titers at (but not above) the cutoff level of 1:400 will be retested for confirmation of titer. Normal values on the second of these tests will be considered to be acceptable for enrollment.

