# 10.6.1 Prophylactic Administration of Prednisone/Prednisolone

All subjects will be discharged from the hospital on oral prednisone or prednisolone at 1 mg/kg/day, which will be adjusted according to IFN-gamma T-cell studies in the following weeks. Subjects will also continue on a PPI until they return to their baseline corticosteroid dose or sooner based on the subject's symptoms and discretion of the sponsor investigator and/or parent.

If the **30 day** post-infusion IFN-gamma T-cell responses to AAV9 and dystrophin show ≤50 SFC per 1 x 10^6 PBMCs, the subject's prednisone or prednisolone dose will be decreased back to the standard clinical dose of 0.75 mg/kg/day. Those subjects who had been on deflazacort may be switched back to the standard clinical dose of 0.9 mg/kg day. For either regimen, approximations of these target doses may be allowed to account for pill formulations (for prednisone and deflazacort), as in clinical practice. If either the AST or ALT exceeds >2.5X the subject's baseline values, and results are confirmed on a follow-up blood test, the prednisone or prednisolone regimen will be maintained at 1 mg/kg/day until the enzyme levels fall within a range, 2.5X the baseline value. Subjects may be asked to undergo a weekly blood test outside of prescheduled visits should the SI deem it necessary to monitor the T-cell response or AST/ALT levels more closely.

If the IFN-gamma T-cell responses show  $\geq 50$  SFC per 1 x  $10^6$  PBMCs, we may increase the dose to approximately 2 mg/kg/day depending on T-cell response measured by ELISpot assay and prolong a subsequent tapering protocol based on the individual subject's immune response profile as assessed by subsequent ELISpot assays (as on the schedule above). Based upon other studies performed at NCH, we anticipate that oral prednisone or prednisolone may be administered for up to 120 days post gene transfer prior to the return to the standard clinical corticosteroid regimen of each subject.

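### The only numerical blood-draw limits for children under 10 kg are percentages of body weight or body volume, not blood volume, and give no practical protection

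*Combined protocol and SAP*

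**What the plan says.** Two places in the combined protocol and SAP give numerical limits on blood draws, both for children under 10 kg.

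- Footnote 15 to Table 8 says the schedule will be reviewed so that draws stay at "≤ 3% of total body weight over a 24 hour period and ≤ 10% of total body weight over a 30 day period".
- Section 9.1.1 (Screening) gives the same 3% and 10%, but of total body volume. It also lets the team move or remove samples not needed for safety when a day's volume would be "too near to 3% of total body volume".

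The revision record (Table 2) shows the purpose of the rule: blood tests may be moved to other days "if the child is under 10kg and may have too much blood drawn". Section 7.1 admits children from just over 6 months of age, so such children are eligible.

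No other section gives a limit in mL, in mL/kg or as a share of blood volume, and no section states the volume drawn at a visit.

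**The concern.** A limit meant to stop too much blood being taken needs blood volume as its base. Here the base is the whole body, under two different names, and neither place corrects the other. Blood is only a small part of the body, so a percentage of the body is a far larger share of the blood.

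The limits have a job to do. Blood is listed at screening and on Days -1, 0, 1, 2, 7, 14 and 30 (Sections 9.1.1 to 9.1.3.3). Section 10.6.1 adds that "Subjects may be asked to undergo a weekly blood test outside of prescheduled visits". If the limits cannot bind, the smallest children have no numerical ceiling on either a day's draw or the 30-day total. The permission in Section 9.1.1 to move or remove samples hangs on the same base, so someone reading it literally would almost never use it.

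**Working it through.** The plan gives only the percentages and derives no figure from them, so there is nothing of its own to reproduce. The check converts the limits to mL/kg and compares them with blood volume.

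**Inputs from the document:** 3% per 24 hours and 10% per 30 days (Table 8 footnote 15; Section 9.1.1).

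**Assumptions, not in the document:** blood volume 70 to 90 mL/kg; density 1.00 to 1.07 kg/L, used to turn a percentage of body weight into mL of blood, or body weight into body volume. Both wordings then give the same range.

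**Step 1. Limits as written, in mL/kg** = percentage × 1000 / density.

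- 24 hours: 0.03 × 1000 / 1.00 = 30; 30 / 1.07 = 28.0.
- 30 days: 0.10 × 1000 / 1.00 = 100; 100 / 1.07 = 93.5.

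**Step 2. Share of the child's blood** = limit in mL/kg / blood volume in mL/kg.

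- 24 hours: 28.0 / 90 = 31.2% to 30 / 70 = 42.9%.
- 30 days: 93.5 / 90 = 103.8% to 100 / 70 = 142.9%.

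**Step 3. The same percentages of blood volume, in mL/kg.**

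- 24 hours: 0.03 × 70 = 2.1 to 0.03 × 90 = 2.7.
- 30 days: 0.10 × 70 = 7 to 0.10 × 90 = 9.
- Ratio of written limit to blood-volume limit: 93.5 / 9 = 10.4 to 100 / 7 = 14.3. The ratio is the same for the 24-hour limit.

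**Step 4. Could the 30-day limit ever bind?** Blood is replenished, so a limit above 100% of blood volume is not impossible to reach. The average daily draw needed is 93.5 / 30 = 3.12 to 100 / 30 = 3.33 mL/kg, every day for 30 days. As a share of blood volume that is 3.12 / 90 = 3.5% to 3.33 / 70 = 4.8% a day.

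**Step 5. An 8 kg child**, whose total blood is 8 × 70 = 560 to 8 × 90 = 720 mL:

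| Limit | As written, density 1.00 | As written, density 1.07 | On blood volume |
|---|---|---|---|
| 24 hours | 240 mL | 224 mL | 16.8–21.6 mL |
| 30 days | 800 mL | 748 mL | 56–72 mL |

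The shares and ratios in Steps 2 and 3 do not depend on the child's weight. Across the whole assumed range the written limits stay more than ten times looser than the same percentages of blood volume.

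**The case against.** The best case on the other side is that this is one wrong word that any pediatric team would read as *blood*, and that its consequence is hypothetical. The listed tests determine how much is drawn; the cap does not. Without volumes per visit, nobody can say that the planned tests would exceed 3% or 10% of blood volume. The schedule is also less dense than a list of days suggests. Blood on Days 0 and 2 is for vector shedding only. Screening may start 45 days before dosing and is split over two visits. The extra weekly tests are discretionary and appear in the text on steroid adjustment after Day 30.

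Few children may be affected. Section 6.3 says "Up to 3 DMD subjects matching the inclusion/exclusion criteria will be enrolled", and Section 4.3.1 puts first symptoms at around age 2 or 3, so a diagnosed child under 10 kg may be uncommon.

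There are other safeguards. The schedule must be reviewed for these children. At screening, "Lab work may be drawn over several days during visit if deemed necessary by study team". For hemoglobin, "subjects will be excluded if they have a value less than the lower limit of normal for age at screening regardless of age". The "Complete blood cell count (CBC) and differential, platelets" is repeated on Days -1, 1, 7, 14, 30 and 60 and at later visits.

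Most of this stands, and it bounds the point: no over-draw is shown, and nothing in the plan is miscalculated; the base is wrong. It does not rescue the limits. The schedule review is directed at these same figures. Spreading screening samples over days does not cap a 30-day total. The hemoglobin rule acts only at screening, and the age ranges shown in Table 7 start at 2 years. Blood counts detect a fall after the blood has been taken. The slip is likely but not proven, since the wording recurs in two forms and no blood-volume figure reveals the intent.

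**Conclusion.** The concern holds. The only numerical blood-draw limits for the smallest children rest on the wrong base and, followed as written, give no practical protection. On the assumed 70 to 90 mL/kg blood volume and 1.00 to 1.07 kg/L density, they allow 31 to 43% of a child's blood in a day and 104 to 143% in 30 days.

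This is an error in operative safety text and should be fixed, but its reach is limited. It affects no endpoint or analysis, and it may apply to none of the subjects enrolled. Confidence is high about the wording and the arithmetic. That *blood volume* was intended is an inference for the sponsor to confirm.

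**What to change.** Once the sponsor has confirmed the base, state the limits in both Section 9.1.1 and Table 8 footnote 15 as 3% per 24 hours and 10% per 30 days of total blood volume. Change the trigger for moving samples in Section 9.1.1 in the same way. Give the blood volume in mL/kg used for the calculation in both places. On 70 to 90 mL/kg the limits become 2.1 to 2.7 mL/kg per 24 hours and 7 to 9 mL/kg per 30 days. A value of 70 to 80 mL/kg is the more cautious choice, at 2.1 to 2.4 and 7 to 8 mL/kg.

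Make the change before any child under 10 kg is screened. It costs two lines of protocol text. Some samples not needed for safety may have to be moved or dropped in these children, which Section 9.1.1 already allows.
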